The purpose of this study is to determine whether sensitizing healthy muscle using capsaicin, a chilli pepper extract, induces a regional change in ultrasound texture features of the targeted muscle, or of the muscles in that are in close proximity. This regional change will be accompanied by electromyography (EMG) recordings to confirm the presence of abnormality. Central sensitization will be induced using topical capsaicin and injectable capsaicin at three different concentrations. This is an exploratory trial that aims to provide preliminary evidence on whether central sensitization is a direct cause of taut band and MTrP development.

Our specific research questions are followings:

- a. Does sensitization cause a significant regional change in the texture features of the targeted muscle or surrounding muscles? Our hypothesis is that there will be a structural change within the sensitized or adjacent muscles.
- b. Does capsaicin induced sensitization elicit a change in motor unit action potential(MUAP) amplitude by approximately 20 to 25% within the region of experimentally induced central sensitization or in the region of texture feature changes? Our hypothesis for this portion of the study is that sensitization modifies the anterior horn cell activity which will be measured by the amplitude of the potentials and the change in texture features.
- c. Does capsaicin induced sensitization elicit continuous electrical activity as observed in MTrPs? This tests the hypothesis that sensitization creates the presence of continuous low amplitude action potentials.
- d. Does capsaicin induced sensitization influence the rate of recruitment of motor units in the muscle within the region induced? Does this occur within the regions identified by the

changes in texture features? The recruitment of motor units is normally expected to follow the Henneman size principle.[20-23] Our hypothesis for this portion of the study is that sensitization will cause an aberration in recruitment. If this is demonstrated, then there is modification of the normal processing at both dorsal and ventral horns of the spinal cord.

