This experimental protocol will be carried out at the [name] Lab, Toronto Rehabilitation Institute to ensure any medical emergencies can be promptly cared for. Following the completion of the preliminary intake forms and participant debriefing, informed consent will be obtained. Each participant will be seated upright with their hands comfortably on their lap in a chair that has a high supportive back. They will be asked to relax their neck and shoulder muscles. A member of the research team will then apply the inclusion and exclusion criteria. The presence of a MTrP will be assessed by palpation of the upper trapezius muscle since this is the current method utilized in clinical practice. If there is a MTrP, then they will be asked to withdraw from the study since they do not satisfy the inclusion and exclusion criteria.

Participants will sit on a chair with one arm extended downward, and with the other arm on an armrest of the chair. The extended arm will be fixed by a wristcuff and a chain down to the floor, with a loadcell between the floor and the end of chain. The loadcell will measure the exerted force. The anatomical location for ultrasound probe and electrode placement will be identified for each participant. The ultrasound probe will be placed on 3 muscles: the trapezius, the supraspinatus, and the infraspinatus. Two ultrasonic pictures will be taken of each. Care will be taken to image the region of the muscle that was not mechanically impacted by the insertion of the needle or injection of the substance. The area will then be cleaned with alcohol and water. The Delsys Galelio surface sensor, and the intramuscular needle electrode will be placed directly on the trapezius' identified area. Participants will be asked to gently contract their trapezius muscle. They will be instructed to perform a gradually increasing contraction in isometric condition, in a controlled manner with a monitor showing the exerted force as well as the target force. They will hold this contraction at 30% of their maximal voluntary contraction, and then

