perform a gradually decreasing contraction to rest. This will be performed four times for each type of study intervention and before as well as after each intervention, namely topical control cream, topical capsaicin at 50ug and 100 ug, injection of the superior aspect of the superior fascia followed by intramuscular injection with these two concentrations of capsaicin. The placement of these latter will be verified by ultrasound guidance. The intramuscular needle will then be removed and participants will be bandaged and cared for appropriately by the expert physician performing the experiment. Following this, ultrasound pictures will be taken again from the same muscles mentioned previously. Participants will be re-examined to determine if there were any adverse effects from the experimental procedures. If any occurred, then these will be carefully managed by the medical members of the research team and recorded. Participants will be asked to remain at the lab for an additional 30 minutes to ensure they are well prior to leaving (Figure 2).

Central sensitization and measurement techniques

Inducing central sensitization

Central sensitization will be induced using capsaicin according to the established technique.[13,24,25] It induces increased pain severity at high doses relative to heat and elicits a dose dependent pain responses, allowing for more easily quantifiable measurements.[26] Capsaicin delivery induces both primary and secondary nociception suggesting that central mechanisms are involved in the nociceptive response, also termed as central sensitization.[13,14] Previous evidence has confirmed that capsaicin can sensitize nociceptive and mechanoheat receptors outside of the region of primary hyperalgesia, with speculation that it can also sensitize chemonociceptive receptors.[13] Therefore, capsaicin can effectively be used to induce central sensitization.

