2. Safety evaluation The investigating physician monitors the patient clinically for signs of distress. The methods and timing for assessing, recording, and analyzing safety parameters. Any signs of distress noted by investigating physician will be assessed clinically and appropriately managed. The information will be recorded on the patient's data form. The study team will discuss all incidents and any potential causal link to the study interventions. Patients will be provided with a contact number for the principal

investigator in order to report any changes that occur during or after the study. Our publication will include a list of any adverse events or intercurrent illness encountered. Any patient who experiences an adverse event will be triaged to their family physician or local emergency department as necessary. They will be contacted after to obtain information on the course of their treatment and the outcome of the event.

3. Sample size calculation.

Using GPower V3.0.10 (Dusseldorf, Germany), considering a medium effect size (Hedge's G) of 0.5 and a moderate correlation coefficients (0.5) among repeated measures, sample size calculation determined that a minimum of 70 participants would be required to detect differences via repeated measures ANOVA (two measurement as before and after among 7 groups) with 80% power and an alpha of 0.05. We aim to recruit 84 participants to account for potential attrition (~20%) of participants given the study duration and frequency of follow-up visits.

We plan to recruit equal number of men and women. To date, there are no reported sex differences in induction of Central Sensitization using Capsaicin among males and females with neurological impairments.

4. Statistical analysis plan

Baseline participants' characteristics including demographics will be analyzed using appropriate descriptive statistics. Mean and standard deviation will be calculated for continuous variables. Categorical variables will be presented as numbers and percentages. To test the change in ultrasound images from baseline to experimental conditions, the

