texture features will be computed in MATLAB and principal component analysis will be computed to reduce the variables. A repeated measures MANOVA will be applied for each intervention group. To test the change in EMG within and between groups a repeated measurement ANOVA will be applied considering each intervention group as a factor. The dependent variable would be considered as pain intensity, duration, and area of pain in separate analysis. Data distributions would be first checked with the Shapiro-Wilk to conform the normal distribution of the data. Additionally, we will test for the homogeneity of variance using Mauchly's test as well as correcting the degrees of freedom if necessary [40]. If the assumption of normality not met, for all skewed data an appropriate transformation will be used. We will construct univariate and multivariable linear regression models of differences in EMG amplitude (differences between after and before) as a function of intervention groups when adjusted for important covariates. Due to small sample size in each group, there is not possible to adjust for several covariates. Therefore, in a univariate model we will find the most important ones. For initial selection of relevant variables, all variables with a p-value ≤ 0.2 in the univariate analysis will be selected and retained in the multivariable analysis.

All Statistical analyses will be conducted with SAS for Windows (version 9.3; SAS Institute, Inc, Cary, NC). Using a two-sided test a P-value ≤ 0.05 will be considered as statistically significant.

Discussion

This will be the first study that assesses the effect of capsaicin induced central sensitization on ultrasound texture features and muscle motor unit activity. Findings from this

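### Ultrasound texture, the first primary outcome, has no stated comparison of capsaicin with control: as written, it is tested for before-after change within each group

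*Combined protocol and SAP*

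**What the plan says.** The Primary Outcomes section lists textural regional change first, and recruitment and amplitude change second. Research question (a) asks: "Does sensitization cause a significant regional change in the texture features of the targeted muscle or surrounding muscles". Study Design calls the trial randomised, placebo-controlled and factorial. The section on inducing central sensitization gives a control for each route: cream base for topical, saline for injection.

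Item 4, the statistical analysis plan, introduces the texture analysis with "To test the change in ultrasound images from baseline to experimental conditions". Texture features are reduced by principal components, and then: "A repeated measures MANOVA will be applied for each intervention group". No other test of texture is described.

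For EMG the wording differs: "To test the change in EMG within and between groups a repeated measurement ANOVA will be applied considering each intervention group as a factor". The regression models also concern EMG only; they take "differences in EMG amplitude (differences between after and before) as a function of intervention groups".

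The Experimental Protocol images three muscles (trapezius, supraspinatus, infraspinatus) with two pictures of each. A surface sensor and a needle electrode are then placed on the trapezius, and participants make ramped contractions to 30% of maximum: "This will be performed four times for each type of study intervention and before as well as after each intervention". After the needle is removed, "Following this, ultrasound pictures will be taken again from the same muscles mentioned previously". Care is to be taken to "image the region of the muscle that was not mechanically impacted by the insertion of the needle or injection of the substance".

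**The concern.** A before-after test within one arm asks whether texture changed. It does not ask whether capsaicin changed it. Between the two imaging sessions other things happen in every arm. The probe is lifted and replaced on all three muscles. The needle electrode and the contraction task act mainly on the trapezius. The instruction to image away from the needle and injection region covers only part of this. The control groups are there to remove such common influences, and the texture analysis as written does not use them.

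At stake is the answer to question (a). If texture shifts in all arms, a significant result in a capsaicin arm could be reported as evidence that sensitization alters muscle structure, although the randomised comparison might show no difference.

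**Working it through.** **1. The two primary outcomes side by side.**

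| | Texture | EMG |
|---|---|---|
| Stated aim | change from baseline | change within and between groups |
| Test | MANOVA for each group | ANOVA with group as a factor |
| Regression on group | none | yes, for amplitude |
| Contrast with control | none stated | group factor stated, contrast not spelled out |

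The difference lies in adjacent sentences of the same paragraph.

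**2. Why the control contrast matters.** Let c be the mean change common to all arms and e the capsaicin effect on a component score. A within-arm test in a capsaicin group examines c + e = 0. The contrast of change, capsaicin minus control, is (c + e) − c = e. The common change cancels only in the second.

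**3. Illustration only.** Assume one component, 12 per group (70/6 = 11.7), no capsaicin effect, and c = 0.5 SD of change. The one-sample noncentrality is 0.5 × √12 = 1.73 on 11 df, so a given capsaicin arm is significant with probability 35%. With five uncorrelated components the figure is 13% if one shifts and 53% if all shift. The control contrast stays at 5%. The values of c, the number of components and their correlation are all assumed; the documents give none.

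**4. The plan's own sample size.** The inputs in item 3 are an effect size of 0.5, correlation 0.5, two measurements, seven groups, 80% power and alpha 0.05, giving 70. Reading 0.5 as f = 0.25 (d/2, two groups) and testing group by time with λ = f² × N × 2/(1 − 0.5), I obtain 62 (63 with equal groups). The 70 is not reproduced, but this point does not depend on it.

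**5. Power of the comparison once it is stated.** At correlation 0.5 the SD of change is SD × √(2 × (1 − 0.5)) = SD, so d = 0.5 applies directly to change on one component. Six groups are assumed, with all capsaicin groups shifting equally.

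- Single dose against its control, noncentrality 0.5 × √(n/2): n = 10 gives 1.12 and 18.5% power; n = 12 gives 1.22 and 21.6%; n = 14 gives 1.32 and 24.7%.
- Both doses pooled within one route: 27.9% (N = 70) to 32.6% (N = 84).
- Pooled over dose and route, noncentrality 0.5/√(1/n₁ + 1/n₂): 46.7 v 23.3 gives 1.97 and 49.3% (N = 70); 56 v 28 gives 2.16 and 56.9% (N = 84).
- Omnibus group by time at N = 70. Four groups at 0.5 and two at 0 have mean 0.333 and SD √[(4 × 0.167² + 2 × 0.333²)/6] = 0.236. Interaction f is half of that, 0.118, so λ = 3.89 and power is 26.2%. If item 3 means interaction f = 0.25, λ = 17.5 and power is 89.1% (six groups) or 86.6% (seven). In this pattern f = 0.25 requires a capsaicin shift of 0.5 × 0.25/0.118 = 1.06 SD.
- The 95% confidence half-width, t × √(1/n₁ + 1/n₂) with pooled error, is 0.75-0.83 SD for a single dose and 0.46-0.51 SD for the fully pooled contrast (N = 84 and N = 70).

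**The case against.** The best defence is that the sentence is loose English for group as a factor. The trial is described as placebo-controlled, both routes have a control, outcomes are to be recorded for each arm, and item 3 sizes the trial by repeated measures ANOVA among 7 groups without limiting it to EMG. The trial also calls itself exploratory. This stands to the extent that the authors may well intend a group comparison. A reader might infer that they mean to ignore the controls for texture; the documents do not support that. But the sample-size sentence names no outcome and describes ANOVA, not the MANOVA planned for texture. Even on the generous reading, no contrast with control is specified.

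A reader might also take the illustrative error rates as this trial's false-positive rate. They are not: they rest on an assumed shift and an assumed number of components. Counting any of four capsaicin arms would raise them further, but that mixes in multiplicity, which alone gives 1 − 0.95⁴ = 18.5% with no shift at all. The common-shift argument is also weaker for supraspinatus and infraspinatus, where probe repositioning is the main shared influence.

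Finally, the control comparison may not be fully randomised even when stated. The section on determination of central sensitization checks each participant before outcomes are measured, withdraws those still not sensitized after a second application, and states no exemption for controls. This is a real limit on the remedy. It does not make within-arm testing adequate.

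**Conclusion.** The point holds as a gap in the stated analysis. For the first primary outcome, the plan as written names only a before-after test within each group, and question (a) would not be answered from the randomised controls. That conclusion rests on the text alone and needs no assumption about the size of a common shift. What is uncertain is whether the wording reflects intent, and how large any common change would be.

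Stating the comparison does not give the trial a well-powered test of a single dose. Omnibus power runs from about 26% to 87-89% at N = 70, depending on how the effect size in item 3 is read, and the documents do not settle that reading. The texture results will mainly be estimates. A contrast pooled over doses and routes gains precision, but a reader should not infer that the design requires it: dose and depth are the two factors the trial sets out to vary.

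**What to change.** Replace the texture sentence with text to this effect:

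- The two images per muscle are averaged. Principal components are computed once, on all groups and both times pooled.
- One repeated-measures MANOVA is fitted to the retained components for each imaged muscle (or with muscle as a factor), with group, time and group by time.
- Any capsaicin claim for texture rests on group by time and on prespecified contrasts of change, capsaicin minus same-route control, with 95% confidence intervals. Within-group changes are descriptive.
- Pooling over doses or routes is optional; if used, it is named in advance.

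Before this can be final, three matters need reconciling:

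- Number of groups: six in the Abstract (four plus two) and in the allocation text of Study Design, nine earlier in Study Design, seven in item 3.
- Control: a topical lotion in Study Design; cream base or saline by route in the section on inducing central sensitization. With a single control group, a same-route contrast would not exist for every arm.
- Whether the withdrawal rule covers controls. If non-sensitized participants are withdrawn, the plan should state that the contrast compares a selected subset and is not fully randomised.

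The cost is analysis-plan wording and these reconciliations, with the same images and software. The limited power shown above should be stated alongside.

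### The stated 80% power is for a seven-group univariate ANOVA and does not cover the first primary outcome, texture, which is most naturally read as tested separately within each group of about 10 to 14 people

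*Combined protocol and SAP*

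**What the plan says.** Primary Outcomes lists regional texture change first and EMG recruitment and amplitude second.

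The Sample size calculation is "considering a medium effect size (Hedge's G) of 0.5" with "a moderate correlation coefficients (0.5) among repeated measures". It gives a minimum of 70 participants for a "repeated measures ANOVA (two measurement as before and after among 7 groups) with 80% power and an alpha of 0.05", raised to 84 for attrition. No other power statement appears.

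The Statistical analysis plan reduces the texture features by principal component analysis and then states: "A repeated measures MANOVA will be applied for each intervention group". The next sentence treats EMG differently: a repeated measures ANOVA for change within and between groups, with group as a factor. The number of retained components is not given, and no texture comparison between groups is described. The threshold for all tests is "Using a two-sided test a P-value ≤ 0.05 will be considered as statistically significant".

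The number of groups varies. The sample size text uses seven; Study Design refers to nine arms and, further on, to six equally allocated groups.

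**The concern.** The study was sized for one test, and its first primary outcome appears to be analysed by another. The sizing test is univariate and uses all participants. The texture test is multivariate and, read plainly, uses only one group at a time. A reader who finds 80% in the sample size section has no figure for the texture test and no means of working one out, because the number of components is open.

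Two things are at stake. First, a change of the planned size could easily be missed in any given group. Second, separate before-after tests make no use of the randomised controls. Post-intervention images follow needle insertion and repeated contractions as well as capsaicin, so a within-group change cannot by itself be attributed to capsaicin.

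**Working it through.** **Inputs.** From the sample size section: g = 0.5, correlation ρ = 0.5, m = 2 measurements, k = 7 groups, α = 0.05. Group sizes: 70/7 = 10; 84/7 = 12; 84/6 = 14 (six groups and no attrition).

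**1. The plan's own figure.** Take f = g/2 = 0.25, the conventional medium value. For the group-by-time interaction, λ = f²·N·m/(1−ρ) = 0.0625 × N × 2/0.5 = 0.25N, on 6 and N−7 df.
- N = 61: 79.9%. N = 62: 80.8%.
- N = 70 (λ = 17.5): 86.6%.

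So 70 is not reproduced; it errs on the large side. The other two effects do not give 70 either: time needs 34 and group needs 170.

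**2. Within-group test, one component.** The paired effect is d = g/√(2(1−ρ)) = 0.5/√1 = 0.5. Power comes from the non-central F on 1 and n−1 df with λ = n·d², which is the two-sided paired t-test.
- n = 10, λ = 2.5: 29.3%
- n = 12, λ = 3.0: 35.3%
- n = 14, λ = 3.5: 41.0%

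For 80%, n = 33 gives 79.5% and n = 34 gives 80.8%, so 34 per group are needed. The change detectable with 80% power is 1.00, 0.89 and 0.81 SD at n = 10, 12 and 14.

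**3. Within-group test, p components.** Use Hotelling's T² through the non-central F on p and n−p df, with λ = n·D². D² = 0.25 if one component changes by 0.5, and 0.25p if all p (uncorrelated) components do.

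| p | One changes: n = 10 / 12 / 14 | All change: n = 10 / 12 / 14 |
|---|---|---|
| 2 | 20.0 / 24.8 / 29.6% | 36.3 / 45.4 / 53.9% |
| 3 | 15.3 / 19.2 / 23.3% | 39.1 / 50.9 / 61.5% |
| 4 | 12.4 / 15.7 / 19.1% | 38.9 / 53.2 / 65.6% |
| 5 | 10.3 / 13.1 / 16.1% | 36.1 / 52.7 / 67.2% |
| 6 | 8.8 / 11.2 / 13.9% | 31.0 / 49.9 / 66.7% |

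The range is about 9% to 67%.

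**4. Sensitivity to the correlation (one component, n = 10 to 14).**
- ρ = 0.3: d = 0.5/√1.4 = 0.423, power 22 to 31%.
- ρ = 0.7: d = 0.5/√0.6 = 0.645, power 45 to 61%.

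**5. What pooling would give.**
- One group's 0.5 SD change with pooled error, F on 1 and N−7 df, λ = (N/7) × 0.25: 34% at N = 70, 40% at N = 84.
- A 0.5 SD difference in change between one active and one control group, F on 1 and 2n−2 df, λ = (n/2) × 0.25: 18.5%, 21.6% and 24.7% at n = 10, 12 and 14.

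**The case against.** The texture sentence is loosely worded and may have meant one MANOVA with group as a factor. That is possible. The differently worded EMG sentence makes separate tests the more natural reading, but does not prove it. If a pooled model was meant, the sentence still needs rewriting, and step 5 shows that power for a single group's change remains low.

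The 80% might also have come from a within-group calculation. If 0.5 was entered as Cohen's f in a one-group before-after test, then λ = 0.25 × 10 × 2/0.5 = 10, n = 10 gives 80.3%, and 7 × 10 = 70. This route cannot be excluded. It implies a paired effect of 1.0, twice the medium g of 0.5 that the plan states, so it does not supply 80% at the stated effect. It is a reason not to affirm that 80% is correct for the pooled ANOVA.

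The plan calls itself exploratory, ties the 80% to an ANOVA, and admits small groups when discussing covariates. All of this stands and limits the weight of the point. A reader might infer that null texture results will be presented as adequately powered; nothing in the text says so.

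A reader might also infer that the MANOVA cannot be computed because the variables could outnumber the participants. Experimental Protocol does say "The ultrasound probe will be placed on 3 muscles: the trapezius, the supraspinatus, and the infraspinatus", but Ultrasound analysis mentions only the trapezius. No number of components is set, and no joint analysis of the muscles is described. The documents do not support that inference.

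**Conclusion.** The point holds as a mismatch between sizing and analysis, not as an arithmetic error in the texture test. No stated power covers the first primary outcome. At the plan's own effect and correlation, one component gives 29 to 41% within a group, and none of the two-to-six-component cases above exceeds about 67%.

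The 29 to 41% should not be read as the power of the planned MANOVA. That power cannot be determined until the number of components and the expected pattern of change are stated.

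The result assumes separate tests by group, a two-sided 0.05 level, and 10 to 14 people per group; nine arms would leave about 8 to 9 and 23 to 26% for one component. Confidence is medium, because it rests on the natural reading of one loosely worded sentence.

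**What to change.** **Statistical analysis plan.** Replace the MANOVA sentence with one repeated measures model for the texture components using all participants, with group as a factor and the group-by-time interaction as the test against control. Fix a small number of components in advance, for example two or three, derived from all participants' baseline images. Report each group's change with a confidence interval.

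**Sample size calculation.** Say that the power figure refers to the repeated measures ANOVA and not to within-group texture tests, and recompute it for the effect and number of groups intended. The current inputs give N = 62 for 80%, or 86.6% at N = 70, for the seven-group interaction on a single outcome. Add the within-group detectable change for one component, about 0.8 to 1.0 SD at 80% power. Note that pooled error raises power for one group's 0.5 SD change only to about 34% (N = 70) to 40% (N = 84).

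**Cost.** Wording and a recalculation, with no extra participants. The stated power for texture becomes less favourable. The single model brings in the randomised controls, but it does not make individual group results precise.

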The Delsys Trigno system, which includes sensors, the Trigno base station, and the EMGworks software will be used to decompose the acquired EMG signals into individual motor units. The following parameters will be analyzed: the firing times and frequency of individual motor units, motor unit action potential amplitude and shapes[36-38], the root mean square value (RMS) of each channel and of the entire signal[16], the coefficient of variation for force steadiness[39], and the centroid of the EMG signal in the cranial-caudal and the medial-lateral directions[16]. This will be repeated for each contraction.

Intramuscular EMG analysis

A 27g monopolar electromyography needle will be placed into the midbelly of the upper fibers of the trapezius muscle using ultrasound guidance. The intramuscular EMG signals will be measured using Cadwell Sierra Wave. Since this system does not offer motor unit decomposition, we will use the intramuscular EMG analysis to provide us with more details of the gross EMG measurements such as the overall RMS value, the coefficient of variation for force steadiness, and the centroid measurements.

Determination of Central Sensitization:

Before measuring outcomes, approximately 20 minutes after capsaicin application we will analyze the area of secondary hyperalgesia for each study subject, then determine whether central sensitization has in fact been induced. The presence of central sensitization is confirmed by expansion of the receptive field and area of secondary hyperalgesia beyond the 25 cm² initial application area. If it has, the study participant will undergo the rest of the experimental methodology. If it has not, the capsaicin will be applied once more and the region of secondary hyperalgesia will be remeasured in 20 minutes later. The above described process for confirming the presence of central sensitization will take place again. If the study participant has not had sensitization at this stage they will be withdrawn from the study.

Primary Outcomes

The primary outcome measures:

1. Textural regional changes
2. Recruitment and Amplitude regional changes

These will be recorded for each arm of the study, please see figure 1.

Secondary outcomes:

1. A record of adverse events

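### No decisive test is named for EMG amplitude, a primary outcome, so a before-after shift shared with the control arms could be read as a capsaicin effect

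*Combined protocol and SAP*

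**What the plan says.** Under Primary Outcomes, the second item is "Recruitment and Amplitude regional changes". Research question b asks: "Does capsaicin induced sensitization elicit a change in motor unit action potential(MUAP) amplitude by approximately 20 to 25" percent. It names no comparator.

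The Statistical analysis plan (item 4) gives three analyses that bear on this outcome:

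- A repeated-measures ANOVA: "To test the change in EMG within and between groups a repeated measurement ANOVA will be applied considering each intervention group as a factor". The next sentence reads: "The dependent variable would be considered as pain intensity, duration, and area of pain in separate analysis". The two sentences do not fit together.
- An unadjusted and a multivariable regression: "We will construct univariate and multivariable linear regression models of differences in EMG amplitude (differences between after and before) as a function of intervention groups".
- A covariate rule for the multivariable model: "all variables with a p-value ≤ 0.2 in the univariate analysis will be selected and retained in the multivariable analysis". No list of candidates is given.

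One threshold covers everything: "Using a two-sided test a P-value ≤ 0.05 will be considered as statistically significant". No section names a primary model, a decisive ANOVA term or an active-versus-control contrast. The Sample size calculation (item 3) mentions only a repeated-measures ANOVA with two measurements and seven groups. It does not say which effect is powered.

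**The concern.** Question b is causal: does capsaicin produce the amplitude change? The planned tests do not all address that.

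- **Time term.** It asks whether the average change over all arms, controls included, differs from zero. Fatigue, needling or drift can make it significant without any capsaicin effect.
- **Group term.** It averages before and after, so it does not test change.
- **Group-by-time term.** It compares change between arms. With two time points and complete data it is algebraically the same test as the unadjusted regression of change on group.
- **Screened regression.** It also compares change between arms, but with covariates chosen from the data, so it can disagree with the unadjusted result.

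A shared shift is plausible. Under Experimental Protocol, four ramped contractions are done before and after each intervention, and a needle electrode is used. The trial has cream-base and saline controls (Inducing central sensitization) that could separate such a shift from capsaicin, but a conclusion drawn from the time term makes no use of them. Because question b has no comparator and the ANOVA sentence covers within-group change, a significant time term could be reported as a positive answer.

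**Working it through.** **Inputs.** From the Sample size calculation: g = 0.5, correlation ρ = 0.5, m = 2 measurements, k = 7 groups, N = 70, 80% power, alpha 0.05. Assumptions: f = g/2 = 0.25, complete normal data, and the shift sizes and number of candidate covariates given below. At ρ = 0.5 the variance of change is 2(1 − 0.5) = 1 in units of one measurement's variance, so an SD of change equals an SD of a single measurement.

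**1. The plan's own figure.** With a noncentral F, λ = f²·N·m/(1 − ρ) for time and group-by-time, and λ = f²·N·m/(1 + ρ) for group.

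- Time and group-by-time: λ = 0.0625 × 70 × 2/0.5 = 17.5.
- Group: λ = 0.0625 × 70 × 2/1.5 = 5.83.

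| Effect (k = 7) | N for 80% power (balanced) | Power at N = 70 |
|---|---|---|
| Time | 34 (35) | 98.5% |
| Group-by-time | 62 (63) | 86.6% |
| Group | 170 (175) | 35.6% |

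None gives 70 (nine groups would give 69 for group-by-time), so the stated N does not reveal which effect was intended.

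**2. Shared shift, no capsaicin effect.** If every arm shifts by d SD of change, the time test has λ = N·d² on 1 and N − k = 63 degrees of freedom, with critical F = 3.99.

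| d | λ | P(time term significant) |
|---|---|---|
| 0.2 | 70 × 0.04 = 2.8 | 38% |
| 0.25 | 70 × 0.0625 = 4.375 | 54% |
| 0.3 | 70 × 0.09 = 6.3 | 70% |
| 0.5 | 70 × 0.25 = 17.5 | 98.5% |

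A common shift cancels from differences between arms, so group-by-time stays at 5%.

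**3. No effect of any kind.** Time and group-by-time are close to independent: 1 − 0.95² = 9.75%. Simulation with N = 70, 7 groups and 6 candidates screened at p ≤ 0.2 gives about 10–13% for at least one of time, group-by-time or the screened regression. The better of the unadjusted and screened regressions alone gives about 5–8% across the settings tried. Each regression by itself holds about 5%.

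**4. Power of between-arm tests of change (SD of change = 1).** For a 0.5 SD difference, the noncentrality is 0.5/√(1/n₁ + 1/n₂).

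- One dose against its control, 10 v 10: 0.5/√0.2 = 1.12, power about 20%.
- Two doses pooled against control, 20 v 10: 0.5/√0.15 = 1.29, power about 25%.

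The 86.6% for the omnibus test is not the same alternative. There λ/N = 17.5/70 = 0.25, so the arm mean changes have an SD of √0.25 = 0.5, which implies a range of at least 1 SD. If instead five active arms all differ from two control arms by 0.5 SD, λ = 70 × 0.25 × (2/7)(5/7) = 3.57 and omnibus power is about 22%.

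**The case against.** **The plan already contains the right comparison.** The trial is randomized and placebo-controlled, and the regression of change on group compares arms. This stands. However, nothing gives that comparison priority over the within-group result.

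**No passage says that the time term would be accepted as support.** Also true. A reader might infer that the plan commits to that reading; it does not. The point is that it leaves the reading open. The documents give no figure for drift or fatigue, so 54% and 98.5% are conditional on assumed shifts.

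**The error rate can be overstated.** A reader might count all three ANOVA F tests plus the screened regression and quote 14–17%. That includes the group term, whereas the ANOVA sentence states its purpose as testing change. Without that term the figure is 10–13%. Nor is disagreement between the two regressions under a true effect (14–21% in simulations with one covariate correlated 0.5 with change) an error rate; it largely reflects the precision gained by adjustment and chance imbalance.

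**Read literally, the ANOVA analyses pain.** The sentence on the dependent variable supports this; the sentence before it says the ANOVA tests EMG. If pain governs, the time-term problem falls away for amplitude and only the regression choice (5–8%) remains.

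**The trial is exploratory.** Several models are normal in that setting. This lowers the severity but does not remove the gap, because a 0.05 rule is applied to declared primary outcomes.

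**Conclusion.** The concern holds in a bounded form. For EMG amplitude the plan has several tests at 0.05 and does not say which answers question b. The serious part is the time term: with no capsaicin effect and an assumed shared shift of 0.25 or 0.5 SD of change, it is significant in about 54% or 98.5% of trials at N = 70 in 7 groups, against 5% for group-by-time. With no effect of any kind, accepting any of the three relevant tests roughly doubles the stated error rate, to about 10–13%. The regression choice alone is a minor matter at 5–8%.

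These figures rest on the ANOVA applying to EMG, on complete normal data and on the assumed shifts and candidate covariates. The change should be made, but the plan is not shown to intend the misreading.

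**What to change.** In the Statistical analysis plan:

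1. Name the group-by-time test (equivalently, the between-group comparison of after-minus-before EMG amplitude) as the single decisive test for question b, at two-sided 0.05, with no covariates or a set fixed in advance.
2. State that the within-group/time and group main-effect terms are descriptive and cannot support a capsaicin effect.
3. Label the regression screened at p ≤ 0.2 a sensitivity analysis that cannot override the decisive test.
4. Follow with active-versus-same-route-control contrasts as supportive estimates with confidence intervals, and state their limited power (about 20–25% at 0.5 SD with 10 per control arm). They should not be the decisive test: there are two if doses are pooled and four if not, so a pooling or multiplicity rule would be needed.
5. Reconcile the sentence naming pain measures as the dependent variable with the ANOVA's stated EMG purpose.

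Before this can be run, the group count must be reconciled: nine arms and six groups under Study Design, seven in the Sample size calculation. Two other points need reconciling with the control arms: the intervention list under Experimental Protocol omits saline, and Determination of Central Sensitization withdraws participants who are not sensitized with no stated exemption for controls.

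The analysis change costs a few sentences and no new data. A before-after change or a favourable secondary model could no longer be presented as support. The omnibus test has about 87% power at the plan's inputs (f = 0.25, N = 70, 7 groups), but that describes a large spread between arms, and power for smaller differences is much lower.
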